4.5.1.2 Investigational Product Inspection

MEDI0382 is supplied as a sterile liquid solution in a prefilled syringe for single use. Each syringe selected for in-clinic treatment administration should be inspected by the unblinded investigational product manager or unblinded study personnel prior to injection. MEDI0382 is supplied at a concentration of 0.5 mg/mL. The solution should not be cloudy, discolored, or contain any visible particles.

Subjects should be instructed to refer to the IFU of investigational product.

If there are any defects noted with the investigational product, the investigator and site monitor should be notified immediately. Refer to the Product Complaint (Section 4.5.1.5) for further instructions.

4.5.1.3 Treatment Administration

In-clinic Treatment Administration

MEDI0382 or placebo should be stored at 2°C to 8°C in the original container. The dose to be administered should be allowed to warm up at room temperature for about 30 minutes before injection. The first day of dosing with MEDI0382 or placebo is considered Day 1. On the day of each dose, investigational product (MEDI0382 or placebo) will be administered according to the schedule of procedures. On study days where fasting is required for an additional assessment, the investigational product (MEDI0382 or placebo) should be taken approximately 2.5 hours prior to the applicable assessment. Investigational product (MEDI0382 or placebo) will be administered by SC injection in the lower abdomen.

Subjects should be instructed to take a whole tablet of dapagliflozin with a half glass of water.

At-home Treatment Administration

Investigational product (MEDI0382 or placebo) should be removed from the refrigerator for at about 30 minutes for temperature equilibration. The subject is not to administer investigational product (MEDI0382 or placebo) if the time outside of the refrigerator has exceeded 8 hours. If the storage time exceeds this limit, a new prefilled syringe should be used. After injection, the subject is to place the used prefilled syringe in the supplied sharps bin. A once-daily dose is to be self-administered by SC injection using the prefilled syringe

as soon as practicable upon waking each morning prior to breakfast. Each prefilled syringe contains only a single dose, and cannot be reused. The subject should be instructed not to reuse the prefilled syringe after administration of the single-dose administration. Subjects should refer to the IFU document for at-home administration details.

If a dose of MEDI0382 or placebo is missed, subjects should take the dose as soon as it is remembered unless it is almost time for the next dose, in which case subjects should skip the missed dose and take the study drug at the next regularly scheduled time.

Subjects should take dapagliflozin (10 mg oral) once daily from the run-in period (for eligible subjects on metformin monotherapy) or randomization (for eligible subjects on dual therapy) until Day 29. Subjects should be instructed to take a whole tablet of dapagliflozin with a half glass of water. If a dose of dapagliflozin is missed, subjects should take the dose as soon as it is remembered unless it is almost time for the next dose, in which case subjects should skip the missed dose and take the study drug at the next regularly scheduled time.

4.5.1.4 Monitoring of Dose Administration

As with any exogenous peptide, allergic reactions to dose administration are possible.

In prior experience with MEDI0382, there has been 1 injection-site reaction and no anaphylactic reactions. During visits to the clinical unit, the site of administration will be checked for signs of injection-site reaction as required (Section 4.3.2.2).

4.5.2 Additional Study Medications

Subjects entering the study must have been treated either with daily, stable doses of oral, blood glucose-lowering therapy with metformin (MTD > 1 gram) monotherapy for at least 8 weeks or stable doses of metformin (MTD >1gram) plus oral dapagliflozin 10 mg once daily dual therapy for at least 3 months prior to screening. Metformin is not provided by the study sponsor.

After screening, eligible subjects on metformin monotherapy will begin an open-label, run-in period on Day -28 and will receive oral dapagliflozin 10 mg per day for 28 days prior to randomization until Day 29. Eligible subjects on dual therapy will receive oral dapagliflozin 10 mg per day from randomization until Day 29.

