3 STUDY DESIGN

3.1 Description of the Study

3.1.1 Overview

This is an exploratory randomized, double-blind, placebo-controlled study to evaluate the efficacy and safety of MEDI0382 versus placebo in overweight/obese subjects with T2DM treated with dapagliflozin and metformin dual therapy.

The study will enroll subjects with T2DM treated either with metformin monotherapy or with metformin and dapagliflozin dual therapy. After the screening period of up to 60 days, subjects treated with metformin monotherapy only will enter a 4-week run-in period where subjects will be administered oral dapagliflozin 10 mg a day, which will be provided by the sponsor. Enrolled subjects that are already treated with metformin and dapagliflozin dual therapy will continue this dual therapy throughout the study and can be randomized after the screening period without entering the run-in period. All subjects (ie, on monotherapy and dual therapy) entering the double-blind treatment period will receive dapagliflozin 10 mg a day, which will be provided by the sponsor.

Forty-six subjects are expected to participate in the study for up to 20 weeks including a screening period of up to 60 days, a 4-week run-in period (for subjects on metformin

monotherapy only), a 4-week treatment period, and a 4-week follow-up posttreatment period. There will be a total of 2 inpatient stays with a duration of 2 to 3 days.

Four-week run-in period

After screening, subjects on metformin monotherapy only will begin an open-label, run-in period on Day -28 and will receive oral dapagliflozin 10 mg a day for 28 days prior to randomization. On Day -14, subjects will return to the clinical unit for an abbreviated physical examination, vital signs, and blood collection for safety laboratory assessments.

Subjects on dual therapy (metformin plus dapagliflozin) can be randomized after the screening period. In addition, all subjects will be given diet and lifestyle advice to follow for the duration of the study.

Four-week treatment period

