4.2.3 Randomized Treatment Period

Table 4.2.3-1 shows all procedures to be conducted from inpatient Visit 4 (Day -2 to Day 1) until the end of the treatment period (inpatient Visit 11, Day 27 to Day 29). Assessments should be performed in the order shown in the table.

Whenever vital signs, 12-lead ECGs, and blood draws are scheduled for the same nominal time, the assessments should occur in the following order: 12-lead ECG, vital signs, and then

blood draws. The timing of the first 2 assessments should be such that it allows the blood draw (eg, PK blood sample) to occur at the exact nominal time.

Table 4.2.3-1 Schedule of Treatment Period Procedures

Study Period	Treatment period											
MEDI0382 Dose level	100 µg			200 µg			300 µg					
Visit Number	V4			V5	V6	V7	V8	V9	V10	V11		
Procedure/ Study Day	-2	-1	1	2	7	8	14	15	22	27	28	29
Inpatient or Outpatient	Inpatient			Outpatient	Outpatient	Outpatient	Outpatient	Outpatient	Outpatient	Inpatient		
Verify eligibility criteria ^a		X										
Admit to clinic	X									X		
Discharge home ^b		X	X									X
Medical and disease history	X											
Physical examination (abbreviated)	X				X		X		X	X		
Body weight ^c			X									X
12-lead digital ECG ^d			X		X		X		X	X		
Vital signs ^e	X		X		X	X	X	X	X		X	X
24-hour ABPM ^f	X						X				X	
Randomization ^g		X	X									
SC injection training ^h	X	X										
Administration of dapagliflozin ⁱ	←-----For the duration of the study-----→											
Administration of metformin ⁱ	←-----For the duration of the study-----→											

Table 4.2.3-1 Schedule of Treatment Period Procedures

Study Period	Treatment period											
MEDI0382 Dose level	100 µg			200 µg			300 µg					
Visit Number	V4			V5	V6	V7	V8	V9	V10	V11		
Procedure/ Study Day	-2	-1	1	2	7	8	14	15	22	27	28	29
Inpatient or Outpatient	Inpatient			Outpatient	Outpatient	Outpatient	Outpatient	Outpatient	Outpatient	Inpatient		
Administration of SC IP (MEDI0382 or placebo) ^j			X	X	X	X	X	X	X	X	X	
Uptitration of SC medication						X		X				
Capillary glucose and ketones monitoring ^k			X			X		X				
Visit requires 10-hour overnight fast the day before arrival ^l		X	X		X		X				X	
Collect Blood samples for:												
Serum chemistry (predose where applicable) ^m	X		X		X		X		X		X	
Serum amylase and lipase (predose where applicable) ⁿ	X				X		X				X	
Serum lactate	X		X		X		X		X		X	
Serum calcitonin	X										X	
pH	X		X		X		X		X		X	
Hematology (predose where applicable) ^m	X		X		X		X		X		X	
MEDI0382 PK ⁿ					X	X	X	X			X	X

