### 2.2 Study Design

This is an exploratory randomized, double-blind, placebo-controlled study to evaluate the efficacy and safety of MEDI0382 versus placebo in overweight/obese subjects with T2DM treated with dapagliflozin and metformin dual therapy. Subjects will participate in the study for up to 20 weeks, including a screening period of up to 60 days, a 4-week run-in period (for subjects on metformin monotherapy only), a 4-week treatment period, and a 4-week post-treatment follow-up period.

The study will enroll subjects with T2DM treated either with metformin monotherapy or with metformin and dapagliflozin dual therapy. After the screening period of up to 60 days, subjects previously treated with metformin monotherapy only will enter an open-label, run-in period where subjects will be administered oral dapagliflozin 10 mg a day for 4 weeks. Enrolled subjects who are already treated with metformin and dapagliflozin dual therapy will continue this dual therapy throughout the study and can be randomized after the screening period without entering the run-in period. All subjects (ie, on monotherapy and dual therapy) entering the double-blind treatment period will receive dapagliflozin 10 mg a day. (Figure 2.2-1)

Figure 2.2-1 Study Flow Diagram

BMI = body mass index; HbA1c = hemoglobin A1c; MTD = maximum-tolerated dose; N = number of subjects; QD = once daily; SC = subcutaneous; T2DM = type 2 diabetes mellitus.

- \* Run-in period only for subjects on metformin monotherapy only at screening
- \*\* Subject on metformin and dapagliflozin dual therapy at screening move directly from screening to double blind treatment period

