#### 3.3.3 Study Drug Exposure

The duration of exposure (number of days dosed) of MEDI0382 and dapagliflozin will be summarized by treatment group with descriptive statistics and by frequency.

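### For subjects who enter on metformin plus dapagliflozin, two protocol sections end dapagliflozin on Day 29 and another carries it through follow-up, while the SAP pools follow-up adverse events with on-treatment ones

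*Protocol*

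**What the plan says.** Two protocol sections end dapagliflozin on Day 29.

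- Section 4.5.2, subjects who enter on dual therapy: "Eligible subjects on dual therapy will receive oral dapagliflozin 10 mg per day from randomization until Day 29".
- Section 4.5.2, run-in subjects: "will receive oral dapagliflozin 10 mg per day for 28 days prior to randomization until Day 29".
- Section 4.5.1.3, a dosing instruction, starts from the run-in period for metformin-only entrants "or randomization (for eligible subjects on dual therapy) until Day 29".

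Other places read differently.

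- Section 3.1.1, on subjects already taking both drugs: they "will continue this dual therapy throughout the study and can be randomized after the screening period without entering the run-in period".
- SAP 2.2 carries the same statement: "dual therapy will continue this dual therapy throughout the study".
- Table 4.2.3-1 labels the dapagliflozin row "For the duration of the study", with no end day.

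On the analysis side, SAP 3.3.3 states: "The duration of exposure (number of days dosed) of MEDI0382 and dapagliflozin will be summarized by treatment group". SAP 3.6.1 counts as treatment-emergent every adverse event after the first investigational product, with no closing date. It also summarizes relationship to MEDI0382 or dapagliflozin. SAP 3.3.2 mentions background diabetes therapy only as a possible baseline descriptor.

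**The concern.** A site treating a subject who entered on dual therapy finds two incompatible instructions for the weeks after Day 29. Depending on the section it follows, the subject comes off MEDI0382 (or placebo) and dapagliflozin almost together, or comes off the injection alone.

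This matters for follow-up safety. The protocol itself says that dapagliflozin lowers fasting glucose and weight (Section 1.1), acts on volume and blood pressure (Section 1.6.3) and may favor ketone production (Section 1.6.4). Follow-up still collects adverse events, vital signs, weight, chemistry, CGM and, for about two weeks, daily finger-prick ketones. A change seen there could reflect withdrawal of one drug or of both, and the planned adverse event tables would not show which. The dapagliflozin exposure summary would also depend on which instruction was followed.

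**Working it through.** **1. The plan's own figure.** No stated figure concerns dapagliflozin duration. The power claim (Protocol 4.8.2: 23 per arm, two-sided 5%, power above 95%) was checked to confirm that it stands apart from this point. Both endpoints have the same standardized effect: 30/20 = 225/150 = 1.5. Power ≈ Φ(1.5 × √(23/2) − 1.96) = Φ(5.087 − 1.960) = 0.9991; the noncentral t with 44 df gives 0.9987. The claim reproduces, and no input involves follow-up.

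**2. The passages side by side.**

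| Place | Run-in subjects | Dual-therapy entrants |
|---|---|---|
| Protocol 4.5.1.3 | to Day 29 | to Day 29 |
| Protocol 4.5.2 | to Day 29 | to Day 29 |
| Protocol 3.1.1 (the sentence on continuing) | not covered | whole study |
| SAP 2.2 (same sentence) | not covered | whole study |
| Table 4.2.3-1 | no end given; table stops at Day 29 | same |

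The clear conflict lies in the right-hand column.

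**3. Does the study include follow-up?** Yes. Section 3.1.1 counts the 4-week posttreatment period within participation, and Section 6.3 ends the study at the last protocol-specified visit. That visit (V13, Table 4.2.4-1) is 28 ± 4 days after the last dose. With the last dose on Day 28 it falls on Day 56, range 52 to 60.

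**4. Dapagliflozin days from Day 1, dual-therapy entrants.** Day 29 rule: 29 days, counting Day 29 as a dosing day. Whole-study rule: 56 days (52 to 60). Difference: 56 − 29 = 27 days (23 to 31). Days 29 to 56 make up 28 of the 56 days in which treatment-emergent events accrue: 28/56 = 50%.

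**5. What follow-up would contain.** If every subject stops, all are off dapagliflozin. If every subject continues, all are on it. If dual-therapy entrants continue and run-in subjects stop, follow-up is mixed by entry therapy. The documents do not say which applies.

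**6. Chance imbalance in the mixed case.** The share entering on dual therapy is not given, and no stratification factor is named (Section 4.6.1). Assume K = 5, 12 or 23 of 46 subjects (about 10%, 25% or 50%) and 23 per arm. The number k in one arm is then hypergeometric (46, K, 23), and the arms differ by at least 20 percentage points when |2k − K|/23 ≥ 0.20. For K = 5 only a 5–0 split qualifies: 2 × C(23,5)/C(46,5) = 2 × 33,649/1,370,754 = 4.9%. For K = 12 the probability is 9.1%, and for K = 23 it is 23.8%. Arms are balanced on average, but a visible imbalance is possible.

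**The case against.** The best defense is that Day 29 ends sponsor supply only. Dual-therapy entrants have already taken dapagliflozin for at least three months, so receiving it from randomization reads like a supply window, and the synopsis and Section 3.1.2 tie supply to the treatment period. Section 3.1.1 would then describe their continuing background therapy. This is plausible for Section 4.5.2 but fits Section 4.5.1.3 poorly, since that section tells subjects what to take. No passage states the distinction. If it was intended, run-in subjects are off dapagliflozin in follow-up and dual-therapy entrants on it, which is the mixed case.

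Much of the rest of the defense stands. Laboratory values and vital signs are summarized by time point, so only adverse events pool the two periods. Concomitant medication is recorded to the end-of-study visit (Section 4.7), so the last dapagliflozin date may be largely recoverable. The SAP names no analysis of follow-up CGM or finger-prick ketones. A formal comparison of arms by dapagliflozin status would have very few events in 46 subjects.

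Four stronger readings are tempting but unsupported.

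- *The conflict covers every subject.* Table 4.2.3-1 is the treatment-period schedule. It marks extensions past Day 29 explicitly for ketones and CGM but not for dapagliflozin, and the follow-up schedule has no dapagliflozin row. Its adverse event row does use the same unqualified phrase and runs on, but those events are listed again in the follow-up schedule. The row adds ambiguity and is weak evidence for run-in subjects.
- *The 70-tablet bottle shows what was meant.* Run-in subjects need 28 + 29 = 57 tablets to Day 29 and 28 + 56 = 84 to Day 56, but the sentence on continuing does not cover them. Dual-therapy entrants need 29 or 56, and one bottle holds either. Bottles per subject are not stated.
- *Follow-up will certainly be mixed.* It will not be if all stop or all continue.
- *Efficacy is compromised.* Section 3.1.1 puts all subjects on dapagliflozin during double-blind treatment, and the named efficacy endpoints end at Day 28 or 29.

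**Conclusion.** The inconsistency is real and unresolved for subjects who enter on metformin plus dapagliflozin. It leaves nominally 27 days of dapagliflozin exposure per such subject undetermined and affects the reading of follow-up safety data and of the exposure summary. It does not touch the Day 28 primary endpoint, the CGM endpoints at Days 7, 14 and 28, or the power. Whether follow-up actually mixes subjects on and off dapagliflozin is conditional, and the number affected cannot be sized because the dual-therapy share is not given. The day counts assume that Day 29 is a dosing day and that the last MEDI0382 or placebo dose is on Day 28. The statistical consequence is modest, but a contradictory dosing instruction is worth correcting at this cost.

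**What to change.** 1. Reconcile Protocol 3.1.1, Table 4.2.3-1, 4.5.1.3 and 4.5.2, and SAP 2.2, to one stated end of dapagliflozin for each entry group. This review takes no view on which end that should be.
2. Make sure the eCRF captures the actual date of the last dapagliflozin dose, whether from study supply or the subject's own prescription.
3. In SAP 3.6.1, tabulate treatment-emergent events with onset up to the last MEDI0382 or placebo dose separately from those starting in follow-up.
4. Show dapagliflozin status, or entry therapy, in the follow-up adverse event listing. A listing is enough; no stratified comparison is needed.

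The cost is wording in five places, at most one date field and one extra table. The small downside is that the follow-up table will hold few events.

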4.5.3 Labeling

Labels for the investigational product will be prepared in accordance with Good Manufacturing Practice (GMP) and local regulatory guidelines. The label will fulfil GMP Annex 13 requirements for labeling. Label text will be translated into local languages, as required.

4.5.4 Storage

All investigational product should be kept in a secure place under appropriate storage conditions. The label on the investigational product kit specifies the appropriate storage.

4.5.5 Treatment Compliance

In-clinic administration

At the clinic, investigational product (MEDI0382 or placebo) is administered by study-site personnel, who will monitor compliance.

At-home administration

Compliance during the at-home dosing period to be monitored via daily diary entries, returned prefilled syringes, and bottles of dapagliflozin. The distribution of investigational product for self-administration should be recorded in the appropriate sections of the eCRF.

4.5.6 Accountability

The investigator's or site's designated investigational product manager is required to maintain accurate investigational product accountability records and will account for all investigational product dispensed to and returned by the subject. Study-site staff, if applicable, or the site monitor delegated to investigational product management will account for all investigational product received at the site, unused investigational product, and for appropriate disposition of investigational product in accordance to local procedures. Upon completion of the study, copies of investigational product accountability records will be returned to MedImmune. All unused investigational product will be returned to a MedImmune-authorized depot or disposed of upon authorization by MedImmune.

In the case of a malfunctioning prefilled syringe, the designated investigational product manager (pharmacist/study nurse) should contact the site monitor delegated to investigational product management to initiate a product complaint process according to Section 4.5.1.5.

4.6 Treatment Assignment and Blinding

4.6.1 Methods for Assigning Treatment Groups

An IXRS will be used for assignment of dapagliflozin tablet bottles (where required), randomization to a treatment group and assignment of blinded MEDI0382 or placebo investigational product kit numbers. A subject is considered randomized into the study when the investigator notifies the IXRS that the subject meets eligibility criteria, and the IXRS provides the assignment of investigational product kit number to the subject.

Eligible subjects will be randomized at a 1:1 ratio following screening to receive either MEDI0382 SC or placebo SC. The IXRS will assign a unique randomization code and treatment group to the subject at each randomization. Subjects who withdraw from the study may be replaced, if deemed necessary by the medical monitor, to ensure that safety data are collected on a sufficient number of subjects.

4.6.2 Methods for Ensuring Blinding

This is a double-blind study in which MEDI0382 and placebo are not identical in the prefilled syringe titration volumes. Neither the subject nor any of the investigator or sponsor staff who are involved in the treatment or clinical evaluation of the subjects will be aware of the treatment received (ICH E9).

The different fill volumes of investigational product (MEDI0382 and placebo) and the relative position of the plunger rods will be visually distinct during administration. To

maintain the blind, investigational product (MEDI0382 and placebo) prefilled syringes will be handled by an unblinded investigational product manager or unblinded study personnel that will not be involved in the treatment or clinical evaluation of subjects. An unblinded qualified designee may administer investigational product to subjects during in-clinic visits. An independent investigational product monitor will also be unblinded to perform investigational product accountability. In the event that the treatment allocation for a subject becomes known to the investigator or other study staff involved in the management of study subjects, the sponsor must be notified immediately. If the treatment allocation for a subject needs to be known to treat an individual subject for an AE, the investigator must notify the sponsor immediately. The site will maintain a written plan detailing which staff members are blinded/unblinded and the process of investigational product administration used to maintain the blind.

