overnight fast for approximately 10 hours. Discharged subjects will return to the clinic on Day 1. Subjects can be randomized after confirming eligibility at any time from Day -1 to Day 1 (predose) to receive either MEDI0382 or placebo. On Day 1, following the overnight fast, dosing of MEDI0382 SC or placebo SC will commence after predose safety measures including but not limited to vital signs, an ECG, and blood collection for laboratory tests (eg, lactate, pH); [REDACTED] dapagliflozin and ketones PK sampling; and measurement of weight are performed. A 24-hour urinary collection for glucose excretion will be collected from Day 1 to Day 2. Subjects will be monitored for safety, glucose, and ketones, and will be discharged from the unit approximately 6 hours postdose. Capillary glucose and ketones monitoring will be done at the site using a glucometer. The subject will return to the unit on Day 2 for safety monitoring and supervision of investigational product administration. The subjects will be discharged with the same syringe pack of investigational product supplies and will continue to self-administer investigational product on an outpatient basis.

[figure not shown]
Subjects will then return to the clinical unit at weekly intervals until a maintenance dose of 300 µg is achieved. Subjects will return to the unit for outpatient visits on Days 7, 8, 14, 15, and 22 to undergo safety assessments including but not limited to an abbreviated physical examination and ECG (Days 7, 14, and 22), vital signs (all visits with ABPM fitted on Day 14 only), urine tests (eg, pregnancy test on Day 14 and Day 22), and blood collection for laboratory tests (Days 7, 14, and 22). MEDI0382, dapagliflozin, and ketones PK sampling will be performed on Days 7, 8, 14, and 15. Uptitration of SC investigational product will occur on Day 8 and Day 15. After uptitration of investigational product, subjects will be monitored for safety, capillary glucose and ketones and will be discharged 6 hours postdose. A 10-hour overnight fast is required prior to visits on Days 7 and 14, and a standardized breakfast meal will be provided 2 hours postdosing on these days. The CGM device will be replaced on Day 14.

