4.5 Investigational Products

4.5.1 Identity of Investigational Product(s)

MedImmune will provide the investigator(s) with investigational product (Table 4.5.1-1) using designated distribution centers.

Table 4.5.1-1 Identification of Investigational Products

Investigational Product	Manufacturer	Concentration and Formulation as Supplied
MEDI0382	MedImmune	Solution for injection in 1.0 mL prefilled syringe, 100 µg per dose, 1 dose
MEDI0382	MedImmune	Solution for injection in 1.0 mL prefilled syringe, 200 µg per dose, 1 dose
MEDI0382	MedImmune	Solution for injection in 1.0 mL prefilled syringe, 300 µg per dose, 1 dose
Placebo	MedImmune	Solution for injection in 1.0 mL prefilled syringe, 1 dose
Dapagliflozin	Bristol-Myers Squibb	10 mg green, plain, diamond shaped, film-coated tablet

MEDI0382 is provided as a sterile liquid drug product (nominal concentration of 0.5 mg/mL) in 50 mM sodium phosphate buffer, propylene glycol 1.85 % w/v, (pH 7.8), and it is intended for SC administration.

Placebo is provided as a sterile solution of 50 mM sodium phosphate buffer, propylene glycol 1.85 % w/v, (pH 7.8), and it is intended for SC administration.

MEDI0382 and placebo will be supplied to the site in blinded kits each containing 8 prefilled syringes. Each kit has a unique number that is printed on all labels within the kit (ie, the outer

carton label and the label of the prefilled syringe within the carton). When supplying the investigational product for at-home dosing, each subject will receive sufficient quantity of drug to last until the next visit, and the kits containing 8 prefilled syringes will be supplied in an additional take-home carton.

Dapagliflozin tablets will be provided in open label bottles containing 70 tablets. The tablets may contain lactose.

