### 2.3 Treatment Assignment and Blinding

An Interactive voice/web response system (IXRS) will be used for assignment of dapagliflozin tablet bottles (where required), randomization to a treatment group, and assignment of blinded MEDI0382 or placebo investigational product kit numbers. A subject is considered randomized into the study when the investigator notifies the IXRS that the subject meets eligibility criteria, and the IXRX provides the assignment of investigational product kit number to the subject.

Eligible subjects will be randomized at a 1:1 ratio following screening to receive either MEDI0382 SC or placebo SC. The IXRS will assign a unique randomization code and treatment group to the subject at each randomization. Subjects who withdraw from the study may be replaced, if deemed necessary by the medical monitor, to ensure that safety data are collected on a sufficient number of subjects.

This is a double-blind study in which MEDI0382 and placebo are not identical in the prefilled syringe titration volumes. Neither the subject nor any of the investigator or sponsor staff who are involved in the treatment or clinical evaluation of the subjects will be aware of the treatment received (ICH E9).

The different fill volumes of investigational product (MEDI0382 and placebo) and the relative position of the plunger rods will be visually distinct during administration. To maintain the blind, investigational product (MEDI0382 and placebo) prefilled syringes will be handled by an unblinded investigational product manager or unblinded study personnel that will not be involved in the treatment or clinical evaluation of subjects. An unblinded qualified designee may administer investigational product to subjects during in-clinic visits.

An independent investigational product monitor will also be unblinded to perform investigational product accountability. In the event that a treatment allocation for a subject becomes known to the investigator or other study staff involved in the management of study subjects, the sponsor must be notified immediately. If the treatment allocation for a subject needs to be known to treat an individual subject for an adverse event (AE), the investigator must notify the sponsor immediately. The site will maintain a written plan detailing which staff members are blinded/unblinded and the process of investigational product administration used to maintain the blind.

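### Do the visibly different MEDI0382 and placebo syringes undo the subject's blind during home dosing?

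*Protocol*

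**What the plan says.** Protocol 4.6.2 and SAP 2.3 carry the same blinding text. The people who are not to know the allocation are given as "Neither the subject nor any of the investigator or sponsor staff who are involved in the treatment or clinical evaluation". The same text says that "MEDI0382 and placebo are not identical in the prefilled syringe titration volumes", and that the fill volumes and "the relative position of the plunger rods will be visually distinct during administration".

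The safeguards described are these:

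- Syringes are handled by unblinded site staff who take no part in treating or evaluating subjects, and "An unblinded qualified designee may administer investigational product to subjects during in-clinic visits" (Protocol 4.6.2).
- Unblinded staff inspect the syringes chosen for clinic dosing (Protocol 4.5.1.2).
- Each site keeps a written plan of who is blinded and how dosing is done so as to keep the blind (Protocol 4.6.2).
- The packaging is masked: "MEDI0382 and placebo will be supplied to the site in blinded kits each containing 8 prefilled syringes" (Protocol 4.5.1). The randomization system handles the "assignment of blinded MEDI0382 or placebo investigational product kit numbers" (Protocol 4.6.1).

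On the placebo itself, Table 4.5.1-1 lists three MEDI0382 strengths but a single placebo entry, "Solution for injection in 1.0 mL prefilled syringe, 1 dose", with no fill volume. Protocol 3.1.1 says "Uptitration of SC investigational product will occur on Day 8 and Day 15", and Protocol 3.1.3 has both MEDI0382 and placebo escalating.

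**The concern.** The plan itself treats the look of the syringe as a threat to the blind, since it brings in unblinded handlers to contain it. That protection stops at the clinic door. Under Protocol 4.5.1.1 and 4.5.1.3 the subject takes the syringe from the refrigerator and injects it, and nothing in either document hides the volume or the plunger at that point. Masked kit labels conceal the name of the product, not its volume.

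If subjects could tell their arm, the outcomes most exposed would be those that depend on belief: reported nausea and other symptoms, and perhaps eating and decisions to stop. Comparing tolerability between arms is a secondary objective (SAP 2.1.2), so a real break in the blind would matter for how that comparison is read.

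**Working it through.** The plan gives no figure of its own on this point, so the check is a count of doses followed by a side-by-side reading.

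**Inputs**

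- 28 once-daily doses: 7 days at 100 µg, 7 at 200 µg, 14 at 300 µg (Protocol 3.1.2).
- Clinic dosing on Days 1, 2, 7, 8, 14, 15 and 28, which is 7 doses; Days 22 and 27 are stated to be home doses (Table 4.2.3-1, footnote j).
- MEDI0382 at a nominal 0.5 mg/mL, that is 500 µg/mL (Protocol 4.5.1).
- Placebo fill: not given. The cases below are assumptions.

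**Home doses**

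28 − 7 = 21, and 21/28 = 75%. By step: Days 3–6 = 4, Days 9–13 = 5, Days 16–27 = 12; 4 + 5 + 12 = 21. This measures how much dosing takes place at home. It does not measure unblinding.

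**Active volumes** (dose ÷ concentration)

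100/500 = 0.2 mL, 200/500 = 0.4 mL, 300/500 = 0.6 mL.

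**Two different counts out of 21 home doses**

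A is the number of home doses whose volume differs between arms. B is the number that follow a missed rise, meaning the subject's own volume failed to go up on Day 8 or Day 15.

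| Placebo fill (assumed) | A | B |
|---|---|---|
| Equal to active at each step | 0 | 0 |
| Rises on Days 8 and 15, at other volumes | up to 21 | 0 |
| Fixed at 0.2 mL | 5 + 12 = 17 | 5 + 12 = 17 |
| Fixed at 0.4 mL | 4 + 12 = 16 | 17 |
| Fixed at 0.6 mL | 4 + 5 = 9 | 17 |
| Fixed at another volume | 21 | 17 |

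17/21 = 81%.

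**Which count matters**

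A subject never sees the other arm's syringe, so A is not a cue to that subject unless they have an outside reference for the active volume. B is the cue a subject could notice alone, and only if they expect a rise and nothing masks its absence. A matters to staff, who see syringes from many subjects, and staff are the people the safeguards in Protocol 4.6.2 are aimed at.

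**Which row the text supports**

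The first row does not fit the plain reading of Protocol 4.6.2, which says the volumes differ. The fixed-fill rows do not fit the natural reading of Protocol 3.1.3, where placebo escalates, and their only support is a table entry that is silent on volume. The second row, a placebo that steps up at volumes other than those of active, fits Protocol 3.1.1, 3.1.3, 4.5.1 and 4.6.2 together. In that row B is 0 of 21.

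**The case for a change.** The strongest case for acting is that it would cost little. A blinding section that admits a visible difference should say what the placebo looks like at each step and how the difference is kept from the person holding the syringe, and a sentence or two would do it. The escalation sentence in Protocol 3.1.3 is written in micrograms, which cannot apply literally to placebo, so it does not prove that the volume rises. If the placebo fill were in fact fixed, 17 of 21 home doses would follow a missed rise, and tolerability is a stated comparison.

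The textual gap stands: neither document gives the placebo fill or a masking measure for home dosing. The inference to a failed blind does not. It needs three things at once: a placebo volume that does not rise, a subject who expects it to, and no masking. The first goes against the more natural reading, and the documents establish none of the three. The detail may well sit in the Instructions for Use, the Investigational Medicinal Product Manual or the site's written plan, all of which the protocol cites for dosing or blinding and none of which was available here.

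The heavier remedies fare worse. New placebo fills would be a manufacturing change whose feasibility cannot be judged from the documents, and they would add nothing against this cue if placebo already steps up. Rewriting the blinding statement to say that subject blinding is not assured would qualify a claim that nothing here shows to be false.

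**Conclusion.** No change to the plan is called for. This is a gap in detail, not a contradiction: the placebo fill and the home masking are left unstated, and every passage on the point fits a placebo that steps up at its own volumes. On that reading, 0 of 21 home doses carry a cue within the subject. The figure of 17 of 21 needs a fixed placebo fill, for which the only support is silence in a table.

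The consequences are limited even if some subjects did guess. The primary endpoint is laboratory glucose AUC from a supervised meal test, so a subject's belief could reach it only indirectly. Adverse events are summarized by group with no between-arm test specified (Protocol 4.8.4.1, SAP 3.6.1). Nausea, seen in up to 41.7% of subjects in an earlier 300 µg cohort (Protocol 3.2.3.2), is itself a cue to treatment that no change of syringe would remove.

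The conclusion assumes that placebo volume rises on Days 8 and 15, as Protocol 3.1.1 and 3.1.3 suggest, and that subjects have no outside reference for the active volume. Confidence is high that the text omits these details and low that any bias results; no bias can be estimated from the documents.
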